## Research Procedures

Describe how the research will be conducted.

- What experience will study participants have?
- What will study participants be expected to do?
- How long will the study last?
- Outline the schedule and timing of study procedures.
- Provide visit-by-visit listing of all procedures that will take place.
- Identify all procedures that will be carried out with each group of participants.
- Describe deception and debrief procedures if deception is involved.

Differentiate between procedures that involve standard/routine clinical care and those that will be performed specifically for this research project. List medications that are explicitly forbidden or permitted during study participation.

What RRT subjects will be asked to do/what happens in the study (in sequential order):

- Blood and effluent will be collected at the start of CRRT, at 48 hours, and on day 7 or ICU discharge, whichever comes first. The blood draw for research is 5 mL per draw.
- At hospital discharge, the patient will undergo a series of muscle strength and function tests including 1)Medical Research Council sum score (MRC-ss), a measure of global peripheral muscle strength that is the current clinical standard for diagnosing ICU-AW, 2) Maximal isometric knee extensor and dorsiflexion muscle strength measured as peak force production and rate of force development, and 3) Maximal isometric grip strength. Muscle power will be measured by the repetitive 5x sit-to stand test a reliable and validate measure of lower-extremity power. Physical function and frailty will be measured using 1) the Short Performance Physical Battery (SPPB), 2) six-minute walk test (6MWT), and 3) Clinical Frailty Scale. SPPB is a performance-based composite test with a total of 12 points including components of balance, chair to stand test, and 4-meter habitual gait speed.

The time period over which procedures will occur:

- Ultrasound will be completed at 2 time points: baseline (CRRT initiation) and 7 days after CRRT initiation OR ICU discharge (whichever comes first)
- Muscle strength/function will be assessed at hospital discharge, and at 1 and 3 months thereafter.

The time commitment for the subject for individual visits/procedures

- The time commitment will be 10-20 minutes for 2 ultrasound procedures as above, and the time needed to collect the research blood and effluent, which is likely to be <10 minutes daily for 7 days or until ICU discharge, whichever is first.
- Muscle strength/function assessment is anticipated to take 30-60 minutes.

Long-term follow-up and how it occurs

- Patients will be seen at 1 and 3 months follow-ups in the outpatient setting. Visit times and dates will be arranged prior to discharge if possible, or via telephone after discharge.

Variables collected from the chart will include the following:

- Demographic data (Age, Gender, Race, BMI)
- SOFA or APACHE score at initiation
- Comorbidities (Charlson Score)
- Cause of AKI (Sepsis, post-surgical, etc.)
- Location of ICU (medical vs surgical)
- Laboratory data at baseline (BMP, CBC, lactate, albumin, INR)
- Daily laboratory data
- % Volume overload at initiation and daily
- CRRT variables (BFR, dose, therapy fluid flow rate, UF, filtration fraction).
- Reason for filter loss
- Time to death (censored for patient drop out or loss to follow up)
- In-hospital Mortality
- Time to renal recovery (censored for interfering events)
- Renal Recovery at hospital discharge

What Control subjects will be asked to do/what happens in the study (in sequential order):

- At hospital discharge, the patient will undergo a series of muscle strength and function tests including 1)Medical Research Council sum score (MRC-ss), a measure of global peripheral muscle strength that is the current clinical standard for diagnosing ICU-AW, 2) Maximal isometric knee extensor and dorsiflexion muscle strength measured as peak force production and rate of force development, and 3) Maximal isometric grip strength. Muscle power will be measured by the repetitive 5x sit-to stand test a reliable and validate measure of lower-extremity power. Physical function and frailty will be measured using 1) the Short Performance Physical Battery (SPPB), 2) six-minute walk test (6MWT), and 3) Clinical Frailty Scale. SPPB is a performance-based composite test with a total of 12 points including components of balance, chair to stand test, and 4-meter habitual gait speed.

The time period over which procedures will occur:

- Muscle strength/function and MKUS will be assessed at hospital discharge, and at 1 and 3 months thereafter.

The time commitment for the subject for individual visits/procedures

- The time commitment will be 10-20 minutes for ultrasound procedures as above, and muscle strength/function assessment is anticipated to take 30-60 minutes.

Long-term follow-up and how it occurs

- Patients will be seen at 1 and 3 months follow-ups in the outpatient setting. Visit times and dates will be arranged prior to discharge if possible, or via telephone after discharge.

Variables collected from the chart will include the following:

- Demographic data (Age, Gender, Race, BMI)
- SOFA or APACHE score at ICU admission

Comorbidities (Charlson Score)

- Cause of respiratory failure (COPD, PNA, etc.)
- Location of ICU (medical vs surgical)
- Laboratory data at baseline (BMP, CBC, lactate, albumin, INR)
- Daily laboratory data

Patients lost to follow-up:

-We will attempt to contact patients prior to their appointment to remind them about the 1 and 3 month visits, and we will attempt telephone contact of patients lost to follow-up.

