
## Objectives

List your research objectives. Please include a summary of intended research objectives in the box below.

Aim 1: Determine the rate and degree muscle wasting in critically ill patients with AKI-RRT vs historic ICU controls without AKI during ICU stay. Hypothesis 1: Patients with AKI-RRT have faster decline in rectus femoris and tibialis anterior muscle size compared to controls .

Aim 2: Determine the trajectory of muscle recovery in patients following an episode of AKI-RRT compared to matched controls by measuring muscle mass, muscle strength and power, and functional status in patients at discharge and at 1 and 3 months thereafter. Hypothesis 2: Patients with AKI-RRT will have a slower trajectory of muscle recovery following ICU discharge compared to matched patients without AKI.

Aim 3: Use trend analysis to determine that changes in plasma amino acid levels on RRT correlate with lean muscle loss during AKI-RRT and predict lack of muscle recovery at 1 and 3 months. Hypothesis 3: Trends in amino acid levels during treatment with RRT will correlate with MKUS determinations of lean body mass in the short-term and will predict lack of muscle recovery at 1 and 3 months.

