This is a prospective, non-blinded, non-randomized study to assess the impact of CRRT on critical illness muscle wasting. As the study is observational and non-interventional in nature, there will be no placebo administered in the course of the study. Patients will be identified based on conversations with ICU and Nephrology consult teams (in addition to chart screening) to determine which patients are likely to receive RRT therapy due to AKI and critical illness. In the first aim, patients will undergo musculoskeletal ultrasound (MKUS) assessments within 24 hours of CRRT initiation, and again at 48 hours and 168 hours. In addition, blood will be drawn at these timepoints and stored for later analysis. In Aim 2, the trajectory of muscle mass recovery will be determined through visits at the time of hospital discharge (to be completed within the hospital), and then at 1 and 3 months thereafter, which will entail separate visits. At these sessions, patients with AKI-RRT and matched controls will undergo measurements of muscle mass, strength, and function at hospital discharge and at 1- and 3-months following discharge. Measurements will include MKUS to determine CSA and muscle echogenicity in the RF and TA muscles. We will evaluate muscle strength by measuring: 1) Medical Research Council sum score (MRC-ss), a measure of global peripheral muscle strength that is the current clinical standard for diagnosing ICU-AW34, 2) Maximal isometric knee extensor and dorsiflexion muscle strength measured as peak force production and rate of force development38, and 3) Maximal isometric grip strength 40. Muscle power will be measured by the repetitive 5x sit-to stand test a reliable and validate measure of lower-extremity power. Physical function and frailty will be measured using 1) the Short Performance Physical Battery (SPPB), 2) six-minute walk test (6MWT), and 3) Clinical Frailty Scale. SPPB is a performance-based composite test with a total of 12 points including components of balance, chair to stand test, and 4-meter habitual gait speed. The 6-MWT assesses the distance a subject can walk in six minutes providing a global marker of physical function and representation of cardiopulmonary endurance. We will summarize descriptive statistics at each timepoint including mean and standard deviation or median and interquartile range, as appropriate. Independent t-tests and Mann-Whitney U tests for non-parametric data will be used as appropriate to compare differences in the testing outcomes between cases and controls at each timepoint. Two-way repeated measures ANOVA will be performed to assess the within change in muscle metrics over time and between group comparisons to understand the trajectories of muscle recovery.

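### The procedure list for RRT subjects schedules no muscle ultrasound at hospital discharge, 1 month or 3 months, although Aim 2 and the Study Design require it

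*Protocol*

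**What the plan says.** **What Aim 2 needs.** Objectives, Aim 2, sets out to describe recovery "by measuring muscle mass, muscle strength and power, and functional status in patients at discharge and at 1 and 3 months thereafter". The Study Design names both groups: "patients with AKI-RRT and matched controls will undergo measurements of muscle mass, strength, and function at hospital discharge", and again 1 and 3 months later. It also fixes the method: "Measurements will include MKUS to determine CSA and muscle echogenicity in the RF and TA muscles". The analysis follows from this: tests between cases and controls at each time point, and "Two-way repeated measures ANOVA will be performed to assess the within change in muscle metrics over time and between group comparisons".

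**What the RRT subjects' list schedules.** Research Procedures says "Ultrasound will be completed at 2 time points: baseline (CRRT initiation) and 7 days after CRRT initiation OR ICU discharge", whichever is earlier. Its line for the recovery visits reads "Muscle strength/function will be assessed at hospital discharge, and at 1 and 3 months thereafter", with no ultrasound. The time-commitment line repeats the count: "The time commitment will be 10-20 minutes for 2 ultrasound procedures as above".

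**What the controls' list schedules.** In the same section, the corresponding line for controls names MKUS alongside strength and function at the same three visits.

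**ICU phase.** The Study Design says "patients will undergo musculoskeletal ultrasound (MKUS) assessments within 24 hours of CRRT initiation, and again at 48 hours and 168 hours", which is three scans. The RRT list gives two.

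**The concern.** Two parts of the current text give the case group different ultrasound schedules, and the shorter one removes every scan that Aim 2 uses. The comparison of muscle-size recovery needs MKUS in both groups at the same visits. If sites work from Research Procedures, controls are scanned at those visits and cases are not. The muscle-size comparison then cannot be made, and no analysis can replace it, because a scan missed at discharge or at 1 or 3 months cannot be taken later.

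Aim 3 is also affected. It asks whether amino acid trends predict lack of muscle recovery at 1 and 3 months, and under the RRT list no ultrasound measure of that recovery would exist in the patients who provide the amino acid data.

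The ICU discrepancy has its own consequences. With two scans, the 48-hour sample has no paired muscle measurement. A patient who dies in the ICU between 48 hours and day 7 contributes no change in muscle size, whereas under the Study Design that patient contributes a 48-hour change.

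**Working it through.** The plan gives no figure to reproduce. The check is a count of the MKUS time points that each section assigns to each group.

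| Time point | Cases, Study Design | Cases, Research Procedures | Controls, Research Procedures |
|---|---|---|---|
| CRRT start / within 24 h | yes | yes | – |
| 48 h | yes | no | – |
| 168 h (day 7) | yes | yes, or ICU discharge if earlier | – |
| Hospital discharge | yes | no | yes |
| 1 month | yes | no | yes |
| 3 months | yes | no | yes |
| **Total** | **6** | **2** | **3** |

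**Recovery visits with MKUS in both groups.** Study Design for cases with the control list: 3 of 3. RRT list with the control list: 0 of 3.

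**Can the RRT list be read as covering the ICU phase only?** No.
1. It also schedules the same subjects' assessments at discharge, 1 month and 3 months, and there it names strength and function alone.
2. It gives the number of ultrasounds as two in two separate places, without limiting it to the ICU.
3. Strength and function cannot be taken to include ultrasound, because the control line lists MKUS separately and the itemised tests contain no imaging.
4. The form's prompt for this section asks for every procedure, visit by visit and group by group.

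Data Collection & Research Materials repeats the lists for both groups and names MKUS for neither, so it does not settle the matter.

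**Case scans at stake (illustrative).** Project Information caps the study at 60 subjects; the share who are cases is not stated. Assume 20, 30 or 40 cases, in-hospital mortality above 50% as the Background gives for AKI-RRT in general, and no loss after discharge.

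Case scans = cases × survival (below 0.5) × 3 visits

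- 20 cases: fewer than 10 survivors, fewer than 30 scans
- 30 cases: fewer than 15 survivors, fewer than 45 scans
- 40 cases: fewer than 20 survivors, fewer than 60 scans

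Under the RRT list the number is 0 in each row.

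**Pairing of ICU samples and scans.** In the Study Design, blood is drawn at the three scan times, so 3 of 3 draws have a scan. In Research Procedures, blood and effluent are taken at CRRT start, at 48 hours, and on day 7 or at ICU discharge. Scans fall at the first and third of these, so 2 of 3 are paired. Each count uses that section's own sampling times. The Study Design mentions blood but not effluent, and its last scan is fixed at 168 hours, so the 3 of 3 does not carry over to effluent or to samples taken at an earlier ICU discharge.

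**The case against.** The strongest reply is that the intent is clear. Aim 2 and the Study Design both require the recovery scans, and the Study Design names AKI-RRT patients. The RRT list never says that ultrasound is omitted at those visits. The lists are also visibly incomplete: the description of what control subjects do leaves MKUS out, although the control timing line schedules it. In addition, this is an IRB application, and it lists a separate protocol file and three stamped consent forms that are not shown; the operative schedule may lie there.

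Part of this stands. The loss of data is conditional on sites following Research Procedures, and the unseen attachment could contain the right schedule. It does not remove the conflict. An explicit count of two, given twice, is more than an item missing from a list, and no other file changes what this document tells a site to do. The modification also adds a third site, which makes a clear schedule more important.

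Two further limits are fair. The scan totals rest on an assumed number of cases and on a background mortality figure that may not fit the enrolled patients, given exclusions such as cirrhosis and recent malignancy. The ICU conflict is a related but separate discrepancy.

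**Conclusion.** The concern holds: the RRT subjects' schedule is wrong as written for Aim 2. It provides MKUS at 0 of 3 recovery visits in cases, where the aim and the design require 3 of 3 and controls have 3 of 3. If it is followed, the between-group tests and repeated measures ANOVA of muscle size cannot be done, and Aim 3 loses any MKUS-based recovery outcome. One outcome domain of Aim 2 is lost, not the whole aim, since strength, power and function are still measured in both groups.

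The 3-versus-0 count comes directly from the text and needs no assumption. The illustrative scan totals are only a guide to scale. The ICU schedule is also contradictory (three scans against two), and the document does not show which version is current. This must be fixed, because the loss is irreversible and the correction is cheap.

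**What to change.** Reconcile Objectives, Study Design, Research Procedures and Data Collection & Research Materials to one assessment schedule.

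- In the RRT subjects' list, add MKUS to strength and function at hospital discharge, 1 month and 3 months, using the wording already in the control list.
- Correct the RRT time-commitment line so that its number of ultrasound procedures matches.
- State one ICU scan schedule, either the three scans of the Study Design or the two of Research Procedures, and use it in both places.
- Name MKUS for both groups in Data Collection & Research Materials.

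**Cost.** An IRB wording change and a check that the three stamped consent forms agree. The scans are non-invasive and fall at visits that cases already attend. The protocol gives 10–20 minutes for two ultrasound procedures without saying whether this is the total or per scan. Three added scans therefore take 3 × (5 to 10) = 15 to 30 minutes if it is the total, or 3 × (10 to 20) = 30 to 60 minutes if it is per scan, for each surviving case, spread over three visits.

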Acute skeletal muscle wasting is a common consequence of critical illness that occurs in up to 65% of patients admitted to the ICU. Critical illness myopathy (CIM), defined as a deficit in muscle size and strength that develops as a result of an ICU admission, is associated with high rates of short- and long-term morbidity and mortality, including decreased quality of life (QoL) due to persistent functional mobility impairments and inability to perform simple activities of daily living. Muscle dysfunction in the critically ill population is driven by underlying changes in cellular and molecular mechanisms leading to a net catabolic state. Rapid reductions in skeletal mass and strength lead to an increased risk of poor patient outcomes, including physical disability and mortality. The diagnosis of CIM in patients with acute respiratory failure or traumatic injury significantly increases the risk of in-hospital and long-term mortality. Recent data suggests that patients lose, on average, 19-27% of rectus femoris muscle size in the first ten days of critical illness. Little is known, however, about the significance of these changes in a subset of critically ill patients with acute kidney injury (AKI) requiring renal replacement therapy (RRT), also known as dialysis. The gold standard for assessing CIM is measurement by muscle biopsy or the analysis of psoas muscle area on a single cross-sectional CT imaging at the level of the L3 vertebra. Musculoskeletal ultrasound (MKUS), a non-invasive alternative, has gained significant traction over the last decade for assessing muscle in patients with critical illness. Studies have demonstrated that MKUS has excellent inter-rater reliability and high clinical utility, and have suggested that MKUS has strong construct validity. Recent data suggests that MKUS can be reliably performed at the ICU bedside, and our preliminary data suggests that graduate students in a healthcare-related field can reliably be trained to assess muscle mass in the ICU using MKUS in as little as 8 hours of training. Changes in rectus femoris size and quality (echo intensity) measured by MKUS were strongly correlated to muscle biopsies in patients with critical illness. In addition, MKUS measures have been shown to have clinical relevance. In a study of 102 surgical ICU patients, muscle wasting determined by MKUS was associated with increased rates of mortality and skilled nursing facility discharge. Acute kidney injury (AKI) is a commonly encountered condition that complicates 22.7% of all inpatient hospital admissions. More than half of all ICU admissions develop AKI, and 13.5% of all ICU patients will require renal replacement therapy (AKI-RRT) during their ICU stay. AKI is associated with poor short- and long-term prognosis. Even Stage 1 AKI is associated with a 10-fold increase in hospital mortality, and AKI-RRT has an in-hospital mortality rate >50%, making AKI-RRT one of the deadliest patient conditions encountered in U.S. hospitals. Even after discharge, patients with AKI continue to have worse outcomes. A meta-analysis of two million patients evaluating outcomes at least a year after admission showed that in-hospital AKI increased the risk of death. Despite how commonly AKI is observed and despite poor long-term outcomes, the rate of outpatient follow-up in this cohort is low. Therefore, patients with AKI are a high-risk, but underserved, group of patients that warrant further study and intervention. AKI of any stage is known to alter tissue utilization of amino acids. Studies have demonstrated that amino acid levels are reduced in AKI, and multiple, non-essential amino acids become conditionally essential. In addition, AKI leads to a state of increased amino acid oxidation, but reduced amino acid transport into muscle. Use of RRT may further exacerbate the issue by removing significant quantities of amino acids from the plasma. Amino acids are small and easily filtered during RRT, so daily losses of amino acids in effluent can be immense at up to 18 grams daily. While cross-sectional analyses demonstrate high clearance levels of amino acids during RRT, there are currently no published longitudinal data regarding amino acid levels. Because skeletal muscle is the major deposit of protein molecules, with nearly 60% of total body protein in humans, we hypothesize that patients with AKI-RRT are at even higher risk of CIM than critically ill controls without AKI.

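### Aim 1 measures muscle loss only in patients who live to a follow-up ICU scan, the two scan schedules disagree on when that scan is, and early deaths have no stated place in the comparison

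*Protocol*

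**What the plan says.** Aim 1 (Protocol, Objectives) is to "Determine the rate and degree muscle wasting in critically ill patients with AKI-RRT vs historic ICU controls without AKI during ICU stay". Hypothesis 1 is that "Patients with AKI-RRT have faster decline in rectus femoris and tibialis anterior muscle size compared to controls".

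The protocol gives two ICU scan schedules for cases:

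- Research Procedures, two ultrasounds: "baseline (CRRT initiation) and 7 days after CRRT initiation OR ICU discharge (whichever comes first").
- Study Design, for the first aim: "assessments within 24 hours of CRRT initiation, and again at 48 hours and 168 hours".

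The Background states that "AKI-RRT has an in-hospital mortality rate >50" percent and that, in a study of 102 surgical ICU patients, "muscle wasting determined by MKUS was associated with increased rates of mortality and skilled nursing facility discharge". For critical illness in general it says that "patients lose, on average, 19-27% of rectus femoris muscle size in the first ten days of critical illness".

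The only analysis methods named (Study Design) are t-tests or Mann-Whitney tests at each timepoint and a two-way repeated measures ANOVA, the latter worded for the recovery trajectories. Time to death and in-hospital mortality are listed among the chart variables for cases, but are not tied to the muscle measure. The chart list for control subjects has no death variable. The enrolment ceiling is 60, with no split into cases and controls.

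**The concern.** A rate of decline needs at least two scans. In Research Procedures the second scan is triggered by day 7 or by ICU discharge, and death is neither. Whoever dies in the ICU first contributes a baseline and nothing more. Tests at each timepoint compare only patients alive then, and a repeated measures ANOVA in its standard form drops anyone with an incomplete set.

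The protocol itself describes a population in which about half or more die in hospital and cites evidence that wasting goes with death. If the patients lost early are the fast wasters, the measured case decline is too small. If more of them are cases than controls, the comparison leans against Hypothesis 1, and a null result could not be told apart from selective loss of the sickest cases. This arises in the first week and is separate from survivorship at the 1- and 3-month visits of Aim 2.

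**Working it through.** The protocol gives no sample size derivation, power or event count for Aim 1, so there is no figure of its own to reproduce. What follows is illustration, with assumptions marked.

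**1. What each schedule leaves for a case who dies in the ICU**

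| Time of death | Research Procedures (2 scans) | Study Design (3 scans) |
|---|---|---|
| Before 48 h | baseline only | baseline only |
| 48 h to 168 h | baseline only | baseline and 48 h |
| After 168 h | complete | complete |

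**2. Share of cases with no follow-up scan**

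Formula: q = in-hospital mortality × share of those deaths before the second scan. Mortality is set at 50%, the protocol's lower bound. The share of deaths that come early is not given and is assumed to be 25-75%.

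- Two-scan schedule: q = 0.50 × 0.25 to 0.50 × 0.75 = 12.5% to 37.5%. If 30 of the 60 are cases (assumed), that is 3.75 to 11.25, or about 4 to 11 patients. At 60% mortality q is 15% to 45%.
- Three-scan schedule, assuming 40-80% of the deaths before day 7 fall after 48 h: 0.125 × 0.20 = 2.5% up to 0.375 × 0.60 = 22.5%.

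**3. Size and direction of the error in mean case decline**

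Formula: understatement = q × (mean loss in early deaths − mean loss in scanned patients).

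The protocol's 19-27% in ten days, scaled linearly to seven, is 19 × 0.7 = 13.3% and 27 × 0.7 = 18.9%, a gap of 5.6 points. Suppose early deaths lose muscle at the top rate and scanned patients at the bottom rate. The understatement is then 0.125 × 5.6 = 0.7 to 0.375 × 5.6 = 2.1 points. With no gap it is 0. With the gap reversed, decline is overstated by 0.7 to 2.1 points.

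**4. Error in the case-control difference**

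Formula, with the same gap in both groups: (q in cases − q in controls) × gap. At 25% vs 5% this is 0.20 × 5.6 = 1.1 points toward no effect. At 25% vs 25% it is 0.

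A fuller version, all inputs assumed: true 7-day loss 16% in cases and 12% in controls, SD 8, and a logistic probability of early death with an odds ratio of 1.5, 2 or 3 per SD of loss. The true difference is 4.00 points. Among patients alive at the scan it becomes:

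| Early deaths, cases vs controls | OR 1.5 | OR 2 | OR 3 |
|---|---|---|---|
| 10% vs 3% | 3.78 | 3.63 | 3.47 |
| 20% vs 5% | 3.53 | 3.24 | 2.92 |
| 35% vs 5% | 3.07 | 2.51 | 1.91 |
| 20% vs 20% | 4.00 | 4.00 | 4.00 |

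In the last row the difference is intact, but mean case decline among survivors is 15.37 to 14.52 instead of 16, so the degree of wasting is still understated by 0.6 to 1.5 points.

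**5. What a mixed model recovers**

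Where the 48-hour scan exists and death depends on the change seen by then (assumed, 20% vs 5% deaths), complete cases give a difference of 3.2 to 3.6, and a likelihood-based analysis of all scans gives about 4.0. A patient with a baseline scan only adds no information on decline under any such model.

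**6. Why death as worst rank cannot be the main analysis**

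Take 35% vs 5% early deaths and no difference in wasting. The probability that a random case ranks worse than a random control is 0.35 × 0.95 + 0.65 × 0.95 × 0.5 + 0.35 × 0.05 × 0.5 = 0.65. With 30 per group (assumed), the expected Mann-Whitney z is (0.65 − 0.5) × 900 / √(900 × 61 / 12) = 135 / 67.6 ≈ 2.0. Excess mortality alone could look like support for Hypothesis 1.

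**The case against.** The strongest reply is that handling of deaths and missing outcomes commonly belongs in a statistical analysis plan, which is not shown, and that the protocol never prescribes a complete-pair analysis for Aim 1. The ANOVA sentence is written in the language of recovery, which is Aim 2. This is a fair limit on the analysis part of the point. It does not dispose of it: the scan times are protocol content, the two sections contradict each other, no analysis plan can supply a scan that was never scheduled, and no other longitudinal method is named.

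A reader might infer that every case dying before day 7 is unscorable. The documents do not support that, because the Study Design section schedules a 48-hour scan. A reader might also infer that case decline is definitely understated. The cited link between wasting and death comes from surgical ICU patients, not AKI-RRT patients, and no rate of loss is given for patients who die early. Nor is a bias toward no effect established: early mortality in the historic controls is not given, and with equal early-death rates the difference is unbiased in the working above. Finally, the figure above 50% is in-hospital mortality, not ICU death before day 7.

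It is also true that the plausible bias works against the hypothesis, so it would not create a false finding of faster wasting, and that at 10% vs 3% early deaths it is only about 0.2 to 0.5 points out of 4.

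**Conclusion.** The point holds in a limited form. On the methods the protocol names, Aim 1 describes patients who reach the later ICU scan, and those who die first drop out of the muscle comparison wholly or in part, depending on which schedule is followed. The group is likely to be material: 12.5-37.5% of cases under the two-scan schedule and 2.5-22.5% under the three-scan schedule, on 50% mortality and the assumed timing of deaths. Understatement of case decline is the plausible direction, on the order of 1 to 2 points of seven-day loss under the assumptions shown, but it is not demonstrated. Attenuation of the case-control difference requires more early deaths in cases than in controls. If that is so, a true 4-point difference could shrink to between 3.8 and 1.9 points across the scenarios with unequal death rates.

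**What to change.** 1. Reconcile the ICU scan schedules in Study Design and Research Procedures, and state what is recorded when a patient dies before a scheduled scan.
2. Analyse Aim 1 with a mixed model for muscle size using all available ICU scans at their actual times, in place of repeated measures ANOVA on complete sets. Say that it recovers information only from patients with at least one follow-up scan, and that it assumes the later course of those who die can be predicted from the scans they had.
3. Report, by group, the number who die before the follow-up scan, using vital status of the historic controls over the same window where it is available. State that the muscle-loss result applies to patients alive at that scan.
4. A joint model of decline and death, or an analysis ranking death as worst, may be added only as a labelled sensitivity analysis. The text should say that worst-rank scoring mixes mortality with muscle loss and can favour Hypothesis 1 through excess deaths alone.

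The cost is analysis wording and a table of counts, with no new visits or patients. Death times are already collected for cases. The one real dependency is whether the historic control data hold early vital status; if they do not, the direction of bias in the comparison cannot be assessed and the report should say so.
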